6.0 TRIAL FLOW CHART

6.1 Initial Treatment Phase with Pembrolizumab

Trial Period:	Screening Phase	Treatment Cycles							End of Treatment	Post-treatment		
		1	2	3	4	5	6	7		Discon	Safety Follow-up	Follow Up Visits
Treatment Cycle/Title:	Screening (Visit 1)								At time of Discon	30 Days Post-discon	Every 9 Weeks Post-discon	Every 12 Weeks
Scheduling Window (Days)^b	-28 to -1	± 3	± 3	± 3	± 3	± 3	± 3	± 3	± 3	± 7	± 7	± 7
Administrative Procedures												
Informed Consent	X											
Informed Consent for Future Biomedical Research (optional)	X											
Inclusion/Exclusion Criteria	X											
Subject Identification Card	X											
Demographics and Medical History	X											
Prior and Concomitant Medication Review	X	X	X	X	X	X	X	X	X	X		
Post-study Anticancer Therapy Status											X	X
Survival Status		<----->										
Clinical Procedures/Assessments												
Review Adverse Events	X	X	X	X	X	X	X	X	X	X	X ^q	
Full Physical Examination	X									X		
Directed Physical Examination		X	X	X	X	X	X	X	X			
Height, Weight, and Vital Signs (T,P,RR,BP) ^c	X	X	X	X	X	X	X	X	X			
12-Lead Electrocardiogram	X											
ECOG Performance Status	X ^r	X	X	X	X	X	X	X	X			
Pembrolizumab Administration		X ^b	X	X	X	X	X	X	X			
LOCAL Laboratory Assessments												
Pregnancy Test ^d	X ^d		X	X	X	X	X	X			X	
PT/INR and aPTT	X ^e											
CBC with Differential ^f	X ^e		X	X	X	X	X		X ^f	X	X	
Chemistry Panel ^f	X ^e		X	X	X	X	X		X ^f	X	X	
Urinalysis ^g	X ^e		X		X		X		X	X		
T3, FT4, and TSH ^g	X ^e		X		X		X		X	X	X	

Trial Period:	Screening Phase	Treatment Cycles							End of Treatment	Post-treatment		
		1	2	3	4	5	6	7		Discon	Safety Follow-up	Follow Up Visits
Treatment Cycle/Title:	Screening (Visit 1)								At time of Discon	30 Days Post-discon	Every 9 Weeks Post-discon	Every 12 Weeks
CENTRAL Laboratory Assessments												
Pembrolizumab Pharmacokinetics ^{h,i}		X ⁱ	X		X		X		X ^{h,i}			
Pembrolizumab Anti-Drug Antibodies (ADA) ^h		X	X		X		X		X ^h			
Blood for Genetics ^j		X										
Whole Blood for Biomarker Studies (serum and plasma) ^k		X										
Whole Blood for Correlative Studies (RNA and DNA) ^k		X	X	X					X			
Tumor Tissue Collection												
Newly Obtained Tumor Tissue ^m		X										
Archival Tumor Tissue ⁿ		X										
Efficacy Measurements												
Tumor Imaging ^o	X ⁱ		X ^o					X ^p		X		

Trial Period:	Screening Phase	Treatment Cycles							End of Treatment	Post-treatment		
		1	2	3	4	5	6	7		Discon	Safety Follow-up	Follow Up Visits

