Treatment Cycle/Title:	Screening (Visit 1)								At time of Discon	30 Days Post-discon	Every 9 Weeks Post-discon	Every 12 Weeks

a. After subjects who experience confirmed site-assessed PD or who start a new anti-cancer therapy, each subject will be contacted by telephone for survival approximately every 12 weeks until the subject withdraws consent, is lost to follow-up, death, or the trial ends. In addition, upon Sponsor request, subjects may be contacted for survival status at any time during the course of the trial.
 
b. Cycle 1 treatment must be given within 3 days of allocation. The window for each visit is \pm 3 days unless otherwise noted.
 
c. Height will be measured at Visit 1 only.
 
d. For women of reproductive potential, a urine or serum pregnancy test should be performed within 72 hours prior to Day 1 of each treatment cycle and 30 days post treatment. A serum test can be done if urine is not appropriate. Additionally, if urine test is positive or is not evaluable, a serum test is required. Subjects must be excluded/discontinued in the event of a positive test results. Pregnancy tests (serum and/or urine tests) should be repeated if required by local guidelines.
 
e. Laboratory tests for screening and determining eligibility are to be performed within 10 days prior to the first dose of trial treatment.
 
f. CBC (Hematology) with diff and Chemistry to be performed every cycle.
 
g. UA and thyroid function tests will be performed every other cycle. T3 is preferred; if not available free T3 may be tested.
 
h. Both PK and Anti-pembrolizumab Samples: pre-dose (trough) PK and anti-pembrolizumab antibody samples will be collected at within 24 hours before infusion at Cycles 1, 2, 4, 6, 8 and every 4 cycles thereafter.
 
i. PK Samples: additional post-dose (peak) PK samples will be drawn within 30 minutes after end of pembrolizumab infusion at Cycles 1 and 8. An additional single PK sample should be drawn at; 24 hours (Day 2), between 72 and 168 hours (Day 4-8) and 336 hours (Day 15) after Cycle 1 dosing.
 
j. Details for collection can be found in Section 7.1.3 Laboratory Procedure/Assessments
 
k. Whole blood samples for correlative studies (DNA and RNA) should be collected pre-dose on Day 1 of Cycle 1, Cycle 2, and Cycle 3, and at treatment discontinuation if subject discontinues prior to Cycle 3. Whole blood for Biomarker Samples (plasma and serum) to be collected pre-dose on Day 1 of Cycle 1 only.
 
l. Screening tumor imaging will be performed within 28 days prior to allocation. Confirmation of baseline measurable disease per RECIST 1.1 by the central imaging vendor is required prior to subject allocation. Confirmation of baseline measurable disease per RECIST 1.1 by the central imaging vendor is required prior to subject allocation.
 
m. Newly-obtained tissue is preferred; FFPE block specimens are preferred to slides. Newly obtained tissue is defined as no intervening treatment (local or systemic) involving the site of tissue biopsy once tissue biopsy is obtained and time of study enrollment.
 
n. Archival tumor tissue will also be requested (where available) to assess the clinical utility of PD-L1 and immune-related GEP assessment in newly obtained vs. archived tissue samples.
 
o. The first on-study imaging time point will be performed at 9 weeks (63 days \pm 7 days) calculated from the date of allocation and will continue to be performed Q9W (63 days \pm 7 days), or earlier if clinically indicated.
 
p. In order to follow irRECIST criteria, if a subject is discontinued from study therapy prior to PD being confirmed at the site then that subject should have tumor imaging performed at the time of treatment discontinuation. If previous tumor imaging was obtained within 4 weeks prior to the date of discontinuation, then additional tumor imaging at treatment discontinuation is not required.
 
q. SAEs will be followed through 90 days following cessation of treatment, or 30 days following cessation of treatment if the subject initiates new anticancer therapy, whichever is earlier
												

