7.1.6.3 Post-Treatment Visits

7.1.6.3.1 Safety Follow-up Visits

The mandatory Safety Follow-up Visit should be conducted approximately 30 days after the last dose of trial treatment or before the initiation of a new anti-cancer treatment, whichever comes first.

All AEs that occur prior to the Safety Follow-Up Visit should be recorded. Subjects with an AE of Grade > 1 will be followed until the resolution of the AE to Grade 0-1 or until the beginning of a new anti-cancer therapy, whichever occurs first. SAEs that occur within 90 days of the end of treatment or before initiation of a new anti-cancer treatment should also be followed and recorded.

Subjects who are eligible for retreatment with pembrolizumab may have up to 2 safety follow-up visits, one after the Initial Treatment Period and one after the Second Course Treatment Phase.

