7.1.6.3.2 Follow-up visits

Subjects who discontinue trial treatment for reasons other than disease progression will move into the Follow-up Phase and should be assessed Q9W by radiologic imaging to monitor disease status. The Sponsor may request survival status to be assessed at additional time points during the course of the study (not to exceed approximately 12 weeks). Every effort should be made to collect information regarding disease status until the start of a new anti-cancer therapy, disease progression, death, or the end of the study.

Information regarding post-study anti-cancer treatment will be collected if new treatment is initiated.

Subjects who are eligible to receive retreatment with pembrolizumab according to the criteria in Section 7.1.6.2 will move from the Follow-up Phase to the Second Course Phase when they experience disease progression.

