7.1.6.3.3 Survival Follow-up

Subjects, who experience disease progression (by site assessment) or start a new anti-cancer therapy, will move into the Survival Follow-Up Phase. Subjects should be contacted by telephone approximately every 12 weeks to assess for survival status until death, withdrawal of consent, or the end of the study, whichever occurs first.

7.1.6.3.3.1 Survival Status

To ensure current and complete survival data is available at the time of database locks, updated survival status may be requested during the course of the study by the Sponsor. For example, updated survival status may be requested prior to but not limited to an external Data Monitoring Committee (eDMC) review, interim and/or final analysis. Upon Sponsor notification, all participants who do not/will not have a scheduled study visit or study contact during the Sponsor defined time period will be contacted for their survival status (excluding participants that have a previously recorded death event in the collection tool).

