7.2.3 Immediate Reporting of Adverse Events to the Sponsor

7.2.3.1 Serious Adverse Events

A serious adverse event is any adverse event occurring at any dose or during any use of Sponsor's product that:

- Results in death;
- Is life threatening;
- Results in persistent or significant disability/incapacity;
- Results in or prolongs an existing inpatient hospitalization;
- Is a congenital anomaly/birth defect;
- Is an other important medical event.

Note: In addition to the above criteria, adverse events meeting either of the below criteria, although not serious per ICH definition, are reportable to the Sponsor in the same timeframe as SAEs to meet certain local requirements. Therefore, these events are considered serious by the Sponsor for collection purposes.

- Is a new cancer (that is not a condition of the study);
- Is associated with an overdose.

Refer to [Table 7](#) for additional details regarding each of the above criteria.

For the time period beginning when the consent form is signed until treatment allocation/randomization, any serious adverse event, or follow up to a serious adverse event, including death due to any cause other than progression of the cancer under study (reference Section 7.2.3.3 for additional details), that occurs to any subject must be reported within 24 hours to the Sponsor if it causes the subject to be excluded from the trial, or is the result of a protocol-specified intervention, including but not limited to washout or discontinuation of usual therapy, diet, placebo treatment or a procedure.

For the time period beginning at treatment allocation/randomization through 90 days following cessation of treatment, or 30 days following cessation of treatment if the subject initiates new anticancer therapy, whichever is earlier, any serious adverse event, or follow up to a serious adverse event, including death due to any cause other than progression of the cancer under study (reference Section 7.2.3.3 for additional details), whether or not related to the Sponsor's product, must be reported within 24 hours to the Sponsor either by electronic media or paper. Electronic reporting procedures can be found in the EDC data entry guidelines. Paper reporting procedures can be found in the Investigator Trial File Binder (or equivalent).

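### The SAE reporting window runs to day 90, but subjects in survival follow-up after progression have no scheduled SAE enquiry after the day-30 visit

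*Combined protocol and SAP*

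**What the plan says.** Section 7.2.3.1 sets the reporting window: "For the time period beginning at treatment allocation/randomization through 90 days following cessation of treatment", cut to 30 days if new anticancer therapy starts. Any SAE in that window, "whether or not related to the Sponsor's product, must be reported within 24 hours to the Sponsor". The trial summary, Section 2.1, and notes q (chart 6.1) and h (chart 6.2) give the same 90 days.

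Section 7.1.6.3.1 schedules the last safety visit that all subjects share: "The mandatory Safety Follow-up Visit should be conducted approximately 30 days after the last dose of trial treatment", or earlier if new therapy begins. It adds that "SAEs that occur within 90 days of the end of treatment or before initiation of a new anti-cancer treatment should also be followed and recorded", but names no contact after day 30 at which to ask.

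The next step depends on why treatment stopped. Under Section 7.1.6.3.2, "Subjects who discontinue trial treatment for reasons other than disease progression will move into the Follow-up Phase", with assessments every 9 weeks. Under Section 7.1.6.3.3, subjects with site-assessed progression, or who start new therapy, go to survival follow-up: "Subjects should be contacted by telephone approximately every 12 weeks to assess for survival status". Note a to chart 6.1 agrees: "each subject will be contacted by telephone for survival approximately every 12 weeks".

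In both charts the row "Review Adverse Events" is marked at the 30-day visit and, with the SAE note attached, at the 9-weekly follow-up visit. The survival follow-up cell is blank.

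Safety is the first secondary objective (Section 3.2). Section 4.2.4.3 lists SAEs among the events to be analysed. Section 8.6.2 and supplemental SAP Section 3.6.2 promise counts and percentages of adverse events.

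**The concern.** The reporting window and the visit schedule do not match. A site that follows the charts exactly has no planned occasion after day 30 to ask a progressed subject about SAEs, although the duty to report them lasts to day 90. Imaging does not fill the gap, because Section 7.1.4.1.3 makes the discontinuation scan the last one required when treatment stops for documented progression.

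The uncovered period matters for this drug class. Section 5.2.1.2 acknowledges that immune-related events can first appear months after dosing has stopped. Section 7.2.3.3 also exempts progression of the cancer from SAE reporting, so in a progressed subject a toxicity event has to be told apart from disease. A call limited to survival status collects nothing that helps with that.

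The trial has one arm, so its safety result is the descriptive count. A non-fatal hospitalisation on, say, day 60 at another hospital could go unrecorded in a progressed subject and be picked up at the next visit in a subject who stopped without progression.

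**Working it through.** The documents state no SAE rate for this period and no share of subjects stopping for progression, so there is no figure of the plan's own to reproduce. The check is a reading of the charts plus calendar arithmetic.

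**1. Chart columns.** Chart 6.1 has 12 columns: screening, seven cycle columns, discontinuation, safety visit, 9-weekly follow-up and survival. The visit-window row has 12 entries. The adverse-event row has 11 marks; the eleventh, carrying note q, falls in 9-weekly follow-up, and survival is empty. Chart 6.2 also has 12 columns and 11 marks, the eleventh carrying note h. Chart 6.1 marks post-study therapy in the survival column. In chart 6.2 those marks appear to sit one column earlier, so the content of the call is less certain there.

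**2. Stopped for progression, no new therapy.** The last scheduled adverse-event review is at day 30 ± 7, that is day 23 to 37.
- Days with no scheduled enquiry: 90 − 30 = 60, and 60/90 = 67%.
- Allowing for the visit window: 90 − 37 = 53 to 90 − 23 = 67 days.

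**3. The survival call.** Twelve weeks is 84 days, with a window of ± 7.
- Counted from discontinuation: day 77 to 91.
- Counted from the safety visit: 30 + 84 ± 7 = day 107 to 121.

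The anchor is not stated. On the first reading the call usually comes before the window closes; on the second it comes after. On neither does it ask about SAEs.

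**4. Stopped without progression.** Nine-weekly visits fall at 63 ± 7 = day 56 to 70 and 126 ± 7 = day 119 to 133, both with adverse-event review marked. The days after the first visit can be picked up retrospectively at the second.

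**5. Started new therapy.** The window can end at day 30, so the gap shrinks or disappears.

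**6. Scenario, on assumed inputs only.** Let f be the share stopping for progression, g the share of those starting new therapy, s the probability of an SAE in days 31 to 90, and m the fraction unreported. Per 100 subjects:

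- Open window and no scheduled enquiry = 100 × f × (1 − g)
- Subjects with a missed SAE = 100 × f × (1 − g) × s × m

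| Assumptions | Open window | Missed |
|---|---|---|
| f = 0.50, g = 0.50, s = 0.05, m = 0.25 | 25 | 0.3 |
| f = 0.83, g = 0.10, s = 0.15, m = 0.50 | 75 | 5.6 |
| any f, g, s, with m = 0 | as above | 0 |

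None of f, g, s or m is given in the documents. The table shows how the result depends on them and is not an estimate.

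**The case against.** The strongest reply is that the duty to collect SAEs already covers everyone. Section 7.2.3.1 requires reporting within 24 hours whichever phase the subject is in, and also requires SAEs judged related to be reported at any time. Section 7.1.6.3.1 says late SAEs are to be followed and recorded. Section 5.8.1 requires data on clinical events after treatment has stopped, and Section 7.1.2.1 allows extra assessments when clinically indicated. This rules out the claim that the SAE count will be incomplete; the text supports only that it may be. It does not remove the point. These provisions govern what a site does with an SAE it knows about, and none creates a contact at which it would learn of one. The plan does put that prompt in the 9-weekly column.

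A reader might infer more in four directions:

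- **That ascertainment depends on response.** It depends on progression status or reason for stopping. A responder who later progresses goes to telephone calls; a non-responder who stops for toxicity gets 9-weekly visits.
- **That at least 57 of 100 subjects are affected.** In the Phase 1b esophageal cohort (Section 4.2.1), 13 subjects had progression as best response (13/23 = 57%; the protocol prints 59%). That is best response in a PD-L1-positive cohort, not reason for stopping. Treatment beyond first progression is allowed here. That progressed subjects are the largest group is plausible, but not stated.
- **That few will leave the window through new therapy.** Section 4.2.1 says there are no standard third-line guidelines, but gives no rate of later treatment.
- **That the 20% to 33% dying between day 30 and day 90 shows the loss.** Exponential survival with the cited medians of 5.2 and 2.4 months gives those figures, but the medians come from second-line trials and count deaths from any cause. Deaths from progression are exempt from SAE reporting, and the survival call finds deaths anyway.

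**Conclusion.** The point holds as a mismatch between the reporting window and the schedule. For subjects in survival follow-up after progression whose SAE window is still open, about 60 of the 90 days have no scheduled SAE enquiry. Non-fatal late SAEs may be under-counted, and ascertainment differs by progression status or reason for stopping.

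The size of the loss cannot be determined from the documents. It could be nil if sites hear of every event without asking. The SAP plans no safety analysis by response or by reason for stopping and there is no comparator arm, so no planned comparison is biased. The ORR results are untouched.

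The conclusion rests on the blank survival cell in both charts, which the column counts support, and on Section 7.1.6.3.3 limiting the call to survival status. This is a cheap improvement to safety data collection, not a flaw in the efficacy design.

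**What to change.** - **Flow charts 6.1 and 6.2:** mark adverse-event review (SAEs only, with note q or h) in the survival follow-up column until the SAE window closes.
- **Section 7.1.6.3.3:** state the date from which the 12-week calls are counted. For subjects whose SAE window is still open, time one call at or just after day 90 after the end of treatment (for example day 90 to 97), asking about SAEs since the 30-day visit. Days with no scheduled enquiry then fall from about 60 to 0 for these subjects.
- **Wording to reconcile in the same amendment:** note a to chart 6.1 speaks of confirmed site-assessed progression, while Section 7.1.6.3.3 does not require confirmation. Sections 7.1.6.3.1 and 7.2.3.1 also word the new-therapy cut-off for SAEs differently.

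The cost is one call re-timed or added per affected subject, one extra question and possibly a few more SAE reports. Only data collection changes; clinical management does not. If too few subjects remain on treatment to justify an amendment, the study report should state that SAEs after day 30 were not actively sought in survival follow-up.

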7.2 Assessing and Recording Adverse Events

An adverse event is defined as any untoward medical occurrence in a patient or clinical investigation subject administered a pharmaceutical product and which does not necessarily have to have a causal relationship with this treatment. An adverse event can therefore be any unfavourable and unintended sign (including an abnormal laboratory finding, for example), symptom, or disease temporally associated with the use of a medicinal product or protocol-specified procedure, whether or not considered related to the medicinal product or protocol-specified procedure. Any worsening (i.e., any clinically significant adverse change in frequency and/or intensity) of a preexisting condition that is temporally associated with the use of the Sponsor's product, is also an adverse event.

Changes resulting from normal growth and development that do not vary significantly in frequency or severity from expected levels are not to be considered adverse events. Examples of this may include, but are not limited to, teething, typical crying in infants and children and onset of menses or menopause occurring at a physiologically appropriate time.

Sponsor's product includes any pharmaceutical product, biological product, device, diagnostic agent or protocol-specified procedure, whether investigational (including placebo or active comparator medication) or marketed, manufactured by, licensed by, provided by or distributed by the Sponsor for human use.

Adverse events may occur during clinical trials, or as prescribed in clinical practice, from overdose (whether accidental or intentional), from abuse and from withdrawal.

Progression of the cancer under study is not considered an adverse event.

All adverse events that occur after the consent form is signed but before treatment allocation/randomization must be reported by the investigator if they cause the subject to be excluded from the trial, or are the result of a protocol-specified intervention, including but not limited to washout or discontinuation of usual therapy, diet, placebo treatment or a procedure. From the time of treatment allocation/randomization through 30 days following cessation of treatment, all adverse events must be reported by the investigator. Such events will be recorded at each examination on the Adverse Event case report forms/worksheets. The reporting timeframe for adverse events meeting any serious criteria is described in section 7.2.3.1. The investigator will make every attempt to follow all subjects with non-serious adverse events for outcome.

Electronic reporting procedures can be found in the EDC data entry guidelines. Paper reporting procedures can be found in the Investigator Trial File Binder (or equivalent).

7.2.1 Definition of an Overdose for This Protocol and Reporting of Overdose to the Sponsor

In this trial, an overdose is any dose higher than ≥ 1000 mg (5 times the protocol-defined dose) of pembrolizumab. No specific information is available on the treatment of overdose of pembrolizumab. In the event of overdose, study treatment should be discontinued and the subject should be observed closely for signs of toxicity. Appropriate supportive treatment should be provided if clinically indicated.

If an adverse event(s) is associated with ("results from") the overdose of Sponsor's product or vaccine, the adverse event(s) is reported as a serious adverse event, even if no other seriousness criteria are met.

If a dose of Sponsor's product or vaccine meeting the protocol definition of overdose is taken without any associated clinical symptoms or abnormal laboratory results, the overdose is reported as a non-serious Event of Clinical Interest (ECI), using the terminology "accidental or intentional overdose without adverse effect."

All reports of overdose with and without an adverse event must be reported by the investigator within 24 hours to the Sponsor either by electronic media or paper. Electronic reporting procedures can be found in the EDC data entry guidelines. Paper reporting procedures can be found in the Investigator Trial File Binder (or equivalent).

